5.1 Inclusion Criteria

In order to be eligible to participate in this study, an individual must meet all of the following criteria:

1. Diagnosis of RA meeting 2010 ACR/EULAR for RA and/or treating MD diagnosis
2. Inadequate response to MTX per treating MD at maximum tolerated dose.
3. Able and willing to provide written informed consent prior to any study specific procedures
4. Age 18 years and above at time of enrollment
5. Subjects not excluded based on race or ethnicity

5.2 Exclusion Criteria

An individual who meets any of the following criteria will be excluded from participation in this study:

1. Participants who are pregnant or are currently breastfeeding
2. History of sensitivity to study compound or any of their excipients
3. Previous intolerance to SCFA or related compounds
4. Current antibiotic treatment (within 3 months of screening) at discretion of PI
5. Current consumption of probiotics (within 3 months of screening) at discretion of PI
6. Severe hepatic impairment (eg, ascites and/or clinical signs of coagulopathy)
7. Renal failure (eGFR <30 or requiring dialysis) by history
8. History of other autoimmune disease at discretion of PI
9. Current immunodeficiency state (e.g., cancer, HIV, others)

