This is being submitted as a separate study from EASi-RA (i20-02068) because of the requirement for participants to have an inadequate response to MTX, while EASi-RA patients are new onset rheumatoid arthritis patients who are rheumatoid arthritis treatment naïve. The patients in this EASi-RAIR study are no longer “new-onset” rheumatoid arthritis compared to the patients in EASi-RA. Additionally, the primary outcomes in both studies are different, therefore necessitating implementation of a new IRB protocol.

Hypothesis

We **hypothesize** that in RA patients with inadequate MTX responses, the oral co-administration of butyrate along with MTX will induce modifications in gut microbial communities that favor a regulatory adaptive immune response that may ultimately increase MTX efficacy.

2.2 Name and Description of the Investigational Agent: Butyrate – a short chain fatty acid

This study is looking at the investigational agent short chain fatty acids (SCFA), and in particular, a four-carbon SCFA called butyrate. Oral butyrate and other oral SCFA mixtures can be found as dietary supplements in local health food shops and pharmacies and are not regulated by the FDA.

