2.2.3 Dose Rationale

Butyrate 1000 mg three times daily will be used in this study. This dose was based on doses found in the literature and over the counter general use guidelines that ranged from 1000mg – 6000 mg daily^{8,10,11}. In our ongoing study in NORA patients, the proposed dosing regimen is feasible, tolerable and promotes changes in gut microbiome diversity (unpublished data).

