2.3 Rationale

MTX is effective in up to only 40-50% of all RA patients yet MTX monotherapy is an anchor drug for most RA patients. It would be beneficial to find a safe, effective and inexpensive oral agent that could increase MTX effectiveness. A major mechanism of MTX is by enhancing Treg function⁴. SCFA have been shown to induce a Treg immune response and induce changes in the gut microbiome in both murine models of inflammatory disease and human patients. Taken together, we propose that an oral SCFA-based supplement given to RA patients on a daily basis along with physician prescribed MTX will induce changes in gut microbial communities that favor a regulatory adaptive immune response. We will analyze gut microbial communities from patients prior to SCFA initiation and evaluate whether SCFA can shift a non-responder gut microbiome into a responder gut microbiome phenotype. We will also analyze blood samples from participants to characterize whether SCFA supplementation leads to increased production of T regulatory cells and regulatory cytokines. We will not have a placebo arm as this is a pilot proof of concept study.

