7.8 Participant Access to Study Agent at Study Closure

The oral SCFA supplement will not be provided after participants are no longer enrolled in the study. If participants are interested in continuing oral supplementation, we will provide information on brand and dosage so that participants can purchase on their own from commercial vendors.

8 Assessment of Safety

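### No look-back excludes current or recent butyrate/SCFA supplement use, so a supplement-group participant's Visit 1 sample may not be pre-treatment

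*Combined protocol and SAP*

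**What the plan says.** Two exclusions in section 5.2 mention the study agent: "History of sensitivity to study compound or any of their excipients" and "Previous intolerance to SCFA or related compounds". Both concern how a person reacted to it, not whether they are taking it. Two other exclusions protect the baseline microbiome: "Current antibiotic treatment (within 3 months of screening) at discretion of PI" and "Current consumption of probiotics (within 3 months of screening) at discretion of PI". Section 5.1 does not require participants to be SCFA-naive.

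No other section closes the gap. Section 4.1 enrols everyone who satisfies the criteria. Section 7.1.1 makes a review of permitted and prohibited medications part of eligibility, but section 7.5 lists no prohibited treatments. Section 7.4 puts over-the-counter products on the case report form, and no eligibility or analysis rule uses that record.

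The agent is easy to obtain outside the trial: section 2.2 says that oral butyrate and SCFA mixtures "can be found as dietary supplements in local health food shops and pharmacies". It is also given in another of the group's studies. Section 2.2.3 states: "In our ongoing study in NORA patients, the proposed dosing regimen is feasible", and reports diversity changes there. Section 2.1 describes EASi-RA as the separate study of new-onset, treatment-naive RA.

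The planned baseline is a sample taken before the agent is started. Section 2.3 says: "We will analyze gut microbial communities from patients prior to SCFA initiation". Section 9.1 treats supplement-group participants as their own controls.

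**The concern.** In a single-group pre-post design, the Visit 1 sample is the only control for the primary endpoint. If a participant is already taking butyrate at Visit 1, the difference between Visits 1 and 2 no longer compares off-agent with on-agent. It compares two on-agent samples, and the expected change shrinks. The secondary changes in serum and fecal SCFA and in Tregs would be diluted in the same way.

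The protocol's own statements suggest that short prior exposure could matter. Section 2.2.1 reports circulating Treg changes within one week of butyrate in healthy volunteers. Section 6.1.9 accepts two weeks of supplementation as enough for an evaluable participant. The plan also already treats two other microbiome exposures in the preceding 3 months as a reason to exclude. The exposure closest to the endpoint is the one left out.

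The main risk is a false negative in a study with almost no spare power. A contaminated baseline cannot be recovered afterwards.

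**Working it through.** **Step 1: can a current user enter under the text as written?** Take a person with RA and an inadequate response to MTX at the maximum tolerated dose, who takes and tolerates shop-bought butyrate.

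- Section 5.1: every inclusion criterion can be met.
- Section 5.2: the sensitivity and intolerance exclusions do not apply, because the product is tolerated. The antibiotic and probiotic exclusions do not apply, because butyrate is neither.
- Investigator discretion: it is attached by name to the antibiotic, probiotic and other-autoimmune-disease exclusions. There is no SCFA-use criterion to which it could attach.
- Section 7.5: nothing is prohibited.
- Section 5.8.1: newly meeting an exclusion criterion allows termination, but SCFA use is not one.

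The person is eligible.

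**Step 2: reproduce the planned sample size.** Inputs from sections 9.1 and 9.2: two-sided Wilcoxon signed-rank test, alpha 0.05, power 80%, d = 0.63 (preliminary) and 0.60 (planning). The method is noncentral-t power for paired differences, with effective size n × 3/π (the efficiency of the signed-rank test under normality) and noncentrality d × √(n × 3/π).

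- d = 0.63, n = 23: effective n = 23 × 0.955 = 21.96; noncentrality = 0.63 × 4.686 = 2.95; power 80.4%.
- d = 0.60, n = 25: effective n = 25 × 0.955 = 23.87; noncentrality = 0.60 × 4.886 = 2.93; power 80.1%.
- d = 0.60, n = 24: power 78.4%.

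The stated 23 and 25 are reproduced, and 25 is the smallest number that reaches 80% at d = 0.60. There is no slack.

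**Step 3: dilution.** Assumptions that are not in the documents: k of the 25 evaluable participants are already on butyrate and have mean change 0; the rest have mean change 0.60; the SD is 1 in both. With f = k/25:

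- mean change = 0.60 × (1 − f)
- SD = √(1 + f(1 − f) × 0.60²)
- diluted d = mean / SD

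Worked for k = 2: f = 0.08; mean = 0.60 × 0.92 = 0.552; SD = √(1 + 0.08 × 0.92 × 0.36) = 1.013; d = 0.545.

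| k of 25 | mean change | diluted d | power, formula | power, simulated signed-rank | evaluable n for 80% |
|---|---|---|---|---|---|
| 0 | 0.600 | 0.600 | 80.1% | 80.1% | 25 |
| 1 | 0.576 | 0.572 | 76.3% | 76.9% | 28 |
| 2 | 0.552 | 0.545 | 72.2% | 72.4% | 30 |
| 3 | 0.528 | 0.518 | 67.9% | 68.4% | 33 |
| 5 | 0.480 | 0.467 | 58.9% | 58.8% | 40 |

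A separate simulation with 20,000 replicates per row differs from the simulated column by at most 0.8 percentage points. The last column keeps the same fraction f as n grows.

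**The case against.** The strongest reply is that the number of such participants is unknown and may be zero. With none, power stays at 80%; with one, it is about 77%. The zero-change assumption is also severe. Section 2.2.3 cites literature and general-use amounts of 1000 to 6000 mg daily, so a person on a low amount could still change. Both points stand, and the table is therefore a conditional range rather than a forecast.

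There are also partial safeguards. Medication history is taken at Visit 1, over-the-counter products are recorded, and serum and fecal SCFA are measured. These might reveal a user and allow a sensitivity analysis. They do not keep the user out or restore a pre-treatment sample.

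Several stronger readings are tempting but not supported:

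- **That EASi-RA participants arrive still on butyrate.** Nothing says they continue it. That EASi-RA is the ongoing butyrate study is itself inferred from sections 2.1 and 2.2.3. Its participants start treatment-naive and must later respond inadequately to MTX at the maximum tolerated dose, so considerable time may pass. Only recent exposure is at issue.
- **That the non-supplement group is contaminated by the same gap.** Section 5.4 defines that group as people who do not want SCFA supplements. Section 9.1 plans no supplement-versus-control comparison; it uses the group to explore shifts after next-line therapy.
- **That section 7.8 creates a route in.** The statement "we will provide information on brand and dosage so that participants can purchase on their own from commercial vendors" concerns people leaving this study, whose baseline has already been taken.
- **That prior tolerators flatter the tolerability results, or that lifetime use must be recorded.** Sections 4.2.1 to 4.2.3 define no tolerability endpoint, and no planned analysis would use lifetime exposure.

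**Conclusion.** The concern holds for the supplement group and for current or recent SCFA supplement use. As written, the criteria admit a person whose Visit 1 stool is not the pre-initiation sample that section 2.3 describes, and the plan already applies look-backs to comparable exposures. The likely direction is dilution of the primary effect. Under the zero-change assumption with d = 0.60 and n = 25, power falls from 80% to about 77%, 72%, 68% and 59% with one, two, three and five users.

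Confidence is high that the criterion is missing. It is much lower about the practical impact, because the documents supply neither the frequency of prior use nor the change to expect in such users. The sample-size calculation itself is correct. The change is worth making because it costs little and a lost baseline cannot be replaced.

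**What to change.** Add one exclusion to section 5.2, applying to the supplement group: *Use of any butyrate or other SCFA supplement, including in another study, within 3 months of screening.* The window is the one already used for antibiotics and probiotics. Someone whose exposure in the new-onset RA study ended earlier than that would remain eligible.

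Ask about this use explicitly in the Visit 1 medication history, so that the criterion is checked and not left to spontaneous mention of a supplement.

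The cost is one amended criterion and one question, with no added visits or samples. A few candidates may be delayed by up to 3 months or lost. The planned 25 evaluable participants need not change.

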5.3 Vulnerable Subjects

Vulnerable subjects will not be enrolled.

5.4 Strategies for Recruitment and Retention

Recruitment

Potential subjects will be informed of the study by their treating physicians. Treating physicians will be informed of the study verbally. Additionally, individuals with inadequate response to methotrexate who do not want to take oral SCFA supplements but rather proceed directly to the next medication their treating physician suggests; are also considered potential subjects, serving as the control group, and will be informed of the study by their treating physician. If patients agree to be contacted for participation, a member of the study team will approach them in person, by phone, via MyChart message. These recruitment materials are uploaded in Research Navigator. The study team also welcomes potential subjects from outside NYULH or Bellevue Hospital who may learn about the study from clinicaltrials.gov or by word-of-mouth.

Once contact is made, subjects will be told the reason they are being contacted and asked if they are interested in participating in this specific study. If the potential subjects agree, the study team will provide them with information regarding the next steps for participation.

If a subject requests information regarding opting out of further recruitment for all research, subjects will be directed to contact study coordinator or have subjects contact [contact] or [name].

Sex of Subjects

Both men and women will be equally recruited into the study. Since RA affects women over men by approximately 3-fold, we will likely recruit more women due to the epidemiology of this disease. There are no enrollment restrictions regarding gender of subject.

Age of Subjects.

Age of the enrolled subjects will be at least 18 years of age.

Racial and Ethnic Origin.

All racial and ethnic groups will be recruited into the study, without any restrictions.

Subject capacity:

Subjects with impaired cognitive capacity will not be consented or enrolled into the study.

Subject comprehension:

If any questions arise, the Study Staff will answer them until the subject has a clear understanding of what is expected if he/she agrees to participate in the study. Each subject will be asked to provide a statement of understanding of the study risks, procedures and what the study entails prior to signing the Study Informed Consent.

Documentation of consent:

Original documents of the Study Informed Consent will be maintained for study purposes and review, if needed.

5.4.1 Use of DataCore/Epic Information for Recruitment Purposes

This study will utilize EPIC to identify subjects.

Datacore may be used for subject recruitment. Subjects will be identified by clinician diagnosis of rheumatoid arthritis and by medications in order to screen for potentially eligible participants who have consented to be contacted for research purposes through their MyChart Study coordinator and Study PI will have access to this information in order to identify and recruit eligible participants.

Study personnel will submit a request to NYULH DataCore via iLab. Study team members who will have access to search results include [name] (sub-I), [name] (research coordinator), [name] (research coordinator) and [name] (research coordinator). The PHI that will be accessed is the clinical diagnosis of the individual, medications, and age. The data will be discarded after use which will include deleting any identifiers that link the individual to the PHI.

The study team will search DataCore/EPIC weekly until recruitment ends.

Treating physicians will be notified of the study through word of mouth.

The patient's primary physician will recommend their patient for the study, after this, the study team will contact the patient by phone or MyChart to gauge their interest,

Any recruitment information sent by email will utilize Send Safe email.

Once potential subjects have been identified, the study team will notify the treating physician (TP) that they have patients eligible to participate as follows:

- Provide TP with an oral script to use when contacting potential subjects
- TP agrees to permit study team to directly contact potential subjects on behalf of TP.
- TP has been notified that the study team will contact potential subjects directly, by letter, phone, email, or the MyChart portal etc.

Once contact is made, approved recruitment language will be used to communicate the reason they are being contacted and subjects will be asked if they are interested in participating in this specific study. Should the potential subjects agree, the study team will provide the subjects with information regarding the next steps for participation.

If a subject requests information regarding opting out of further recruitment for all research, subjects will be directed to contact [contact] or [name].

5.5 Informed Consent Process**5.5.1 Consent/Assent and Other Informational Documents Provided to Participants**

Consent forms describing in detail the study agent, study procedures, and risks are given to the participant and written documentation of informed consent is required prior to starting any research activities. The consent form is submitted with this protocol.

5.5.2 Consent Procedures and Documentation

Informed consent is a process that is initiated prior to the individual's agreeing to participate in the study and continues throughout the individual's study participation. Extensive discussion of risks and possible benefits of participation will be provided to the participants and their families. Consent forms will be IRB-approved and the participant will be asked to read and review the document. The investigator will explain the research study to the participant and answer any questions that may arise. All participants will receive a verbal explanation in terms suited to their comprehension of the purposes, procedures, and potential risks of the study and of their rights as research participants. Participants will have the opportunity to carefully review the written consent form and ask questions prior to signing. The participants should have the opportunity to discuss the study with their

surrogates or think about it prior to agreeing to participate. The participant will sign the informed consent document prior to any procedures being done specifically for the study. The participants may withdraw consent at any time throughout the course of the trial. A copy of the signed informed consent document will be given to the participants for their records. The rights and welfare of the participants will be protected by emphasizing to them that the quality of their medical care will not be adversely affected if they decline to participate in this study.

A copy of the signed informed consent document will be stored in the subject's research record. The consent process, including the name of the individual obtaining consent, will be thoroughly documented in the subject's research record. Any alteration to the standard consent process (e.g. use of a translator, consent from a legally authorized representative, consent document presented orally, etc.) and the justification for such alteration will likewise be documented.

When a participant consents to this study, his/her name, address, phone numbers, DOB, and copies of medical records will be collected and kept with the informed consent. At this time, he/she will be assigned a unique study identification number. All subsequent data analysis, specimen recording, and samples will be encoded with this identification number, only and the date of collection. No personal identifiers will be displayed. The principal investigator/project administrator will keep the original, signed informed consents in a locked cabinet in a locked office together with records of specimens donated and medical record copies secured for review. Information with participant names will not be used in any publications resulting from this investigation. The PI will retain the participant contact information until the conclusion of the study.

5.6 Duration of Study Participation

The duration of participation will be approximately 2 months with option to extend for additional visit up to 12 months after month 2 visit.

5.7 Total Number of Participants and Sites

Recruitment will end when approximately 65 participants are enrolled. It is expected that approximately 65 participants will be enrolled in order to produce 25 evaluable participants. Participants will be recruited from NYULH and Bellevue. The study team may also enroll any potential candidate from outside NYULH or Bellevue who contacts the study team. There will be no international site recruitment.

5.8 Participant Withdrawal or Termination

5.8.1 Reasons for Withdrawal or Termination

Participants are free to withdraw from participation in the study at any time upon request. An investigator may terminate participation in the study if:

- Any clinical adverse event (AE), laboratory abnormality, or other medical condition or situation occurs such that continued participation in the study would not be in the best interest of the participant
- The participant meets an exclusion criterion (either newly developed or not previously recognized) that precludes further study participation

5.8.2 Handling of Participant Withdrawals or Termination

Any participant can withdraw his/her informed consent for the research use of their donated blood specimen and revoke his/her Authorization for the use and disclosure of his/her protected health information at any time and without any penalty. In this case, any unused specimens that have not been provided to the researchers will be destroyed. The NYU Langone Health research staff and System Administrator have received training in Good Clinical Practice and understand issues of patient/participant confidentiality. Given the fact that the research studies to be conducted are experimental and are not clinically validated, participants will not be notified of their tests results performed in the future.

5.9 Premature Termination or Suspension of Study

This study may be temporarily suspended or prematurely terminated if there is sufficient reasonable cause. Written notification, documenting the reason for study suspension or termination, will be provided by the suspending or terminating party to [name], the funding agencies, and regulatory authorities. If the study is prematurely terminated or suspended, the PI will promptly inform the NYU IRB and will provide the reason(s) for the termination or suspension.

Circumstances that may warrant termination or suspension include, but are not limited to:

- Determination of unexpected, significant, or unacceptable risk to participants
- Demonstration of efficacy that would warrant stopping
- Insufficient compliance to protocol requirements
- Data that are not sufficiently complete and/or evaluable
- Determination of futility

Study may resume once concerns about safety, protocol compliance, data quality are addressed and satisfy the sponsor and/or the NYU IRB.

Patients who are discontinued from study compound for any reason other than an SAE will be encouraged to remain on the study (not be officially withdrawn from the study) and complete all study visits. The data obtained will be used to understand variations in microbiome and Treg after discontinuation of SCFA.

6 Study Agent (Study drug, device, biologic, vaccine etc.) and/or Procedural Intervention

